#### 8.2.3.2 Recruitment

The details of parents who have consented for potential participation in interviews will be passed on to the qualitative researcher who will be conducting the interviews. The researcher will contact eligible parents approximately 2 to 3 months after PICU transport to confirm that they still wish to participate, answer any questions they might have about the study, and arrange a mutually convenient time and location for the interview to take place. Further written consent will be obtained at the time of interview to confirm that parents agree to participate and for their interview to be recorded. Interviews will be conducted face to face wherever possible, but if parents prefer, telephone or Skype interviews will also be facilitated. If necessary, interpreters will be arranged to ensure that non-English speaking families are able to participate if they wish.

#### 8.2.3.3 Interviews

As described above, we aim to recruit parents of approximately 50 children/young people transported to PICU. This number will enable us to interview parents who represent each of the retrieval models from different PICRTs, thus allowing us to capture important elements of the experience of different models, whilst at the same time ensuring that the number of interviews is feasible to conduct and analyse in the time available. The interview guide will focus on parents' experiences prior to, during, and after transport to PICU with the aim of obtaining a more in-depth understanding than will be possible from the questionnaires. Particular areas of focus will aim to understand what specific aspects of the retrieval parents (and/or children) experienced as working well; what they think would constitute an 'ideal' or optimum transport to PICU; what aspects participants felt worked less well and what could have been done to improve their experience. The interviews will provide greater insight into what a 'high quality' retrieval looks like from the perspective of parents. Interviews are expected to last between 1-2 hours, with appropriate breaks

if necessary, recognising that parents will be revisiting a difficult and upsetting time in their lives. Interviews will be audio-recorded and transcribed verbatim.

#### 8.2.4 CHILDREN'S AND YOUNG PEOPLE'S PERSPECTIVES

Where feasible, children and young people will also be recruited to provide feedback about their experiences during transfer to PICU. Whilst it is acknowledged that the majority of children/young people will be too young and/or too ill at the time to recollect their transfer to PICU, there may be some who will be able and willing to share their experiences.

#### 8.2.4.1 Sampling

We will endeavour to use a diverse sampling strategy to recruit 20-30 children/young people from across the different PICRTs (although if it feasible to recruit up to 5 from each of the 10 PICRTs we will do so), focusing on recruiting children who were transported to PICU for different underlying reasons and via different PICRT models. Whilst we hope that there will be diversity within the sample in terms of elements such as urban/rural location, main diagnosis, and existing/new condition, we are also aware of the challenges of recruiting eligible children, so our recruitment strategy will be more flexible. We envisage that most, but not necessarily all, will be children of parents recruited for interviews.

#### 8.2.4.2 Recruitment

Children and young people will be eligible for recruitment if they fulfil the following criteria:

- Aged between 5 and 16 years
- Able to remember at least some of their transfer to PICU
- Able to provide age-appropriate assent for their participation
- Parent(s) has provided consent for their child's participation

Recruitment of children will be along similar lines as described above, except that written assent will be obtained from children for their own participation, using an age-appropriate assent form.

#### 8.2.4.3 Interviews

We will use a range of creative methods to engage children/young people, including activities such as 'draw and write', [21] 'Talking mats', [22] and third-person craft activities, and a conversation will be developed around the use of these materials. Sessions will be audio-recorded, photographs taken of any creative outputs and notes made immediately after the session about aspects such as the children's engagement, ability to recall and impact of revisiting the time of their transport to PICU. We will explore with the children their experiences of being transported to PICU, dependent on what they can recall, focusing on the time before, during and immediately after the transfer. Recognising that this is likely to have been a distressing time for children, the researcher will be particularly sensitive to, and careful about, how these experiences are explored. If children would like their parents to be present, this will be facilitated. Sessions are expected to last 30-60 minutes, to enable time for rapport building with children at the start of the session and some appropriate "ending" of the session before they leave. Members of the research team have experience of using creative methods and interviewing children, and any training in the use of specific methodologies will be provided to the researcher.

#### 8.2.5 CLINICIAN AND SERVICE MANAGER PERSPECTIVES

#### 8.2.5.1 Sampling

We will use a purposive sampling strategy to identify and recruit 35-40 healthcare professionals from PICRTs, PICUs and acute general hospitals. Use of a sampling matrix will ensure diversity in terms of professional background, experience, place of work (local hospital, dedicated transport team, PICU-run transport team, PICU), rural/urban location and number of emergency transfers. We will also recruit 4-8 service managers/NHS commissioners for interviews.

#### 8.2.5.2 Recruitment

Local PIs at PICRTs will be asked to identify at least 5-6 eligible professionals from within their own service, the PICUs they serve, and acute general hospitals in their region, as well as local service managers/commissioners. Study information and an invitation letter to participate in the interview will be provided to eligible participants. If they are willing to participate, participants will be asked to consent to their details being passed to the researcher who will be conducting the interviews. On receiving the details, the researcher will contact them to check that they still wish to participate, answer any questions they have about the study and arrange a mutually convenient time for the interview to take place. Professionals will be offered the opportunity to participate in a telephone or face-to-face interview, depending on their preference. Prior to the interview commencing the researcher will ask the professional to provide further consent confirming agreement to participate and for recording the interview.

#### 8.2.5.3 Interviews

Semi-structured interviews will be conducted to elicit staff experiences and perceptions of the transport of critically ill or injured children/young people, the impact of the service on the care provided to the children/young people themselves, and any wider impact on other patients and services. A topic guide will be developed based on relevant literature and the experience of the study team/steering group, and will be piloted with 3-4 clinicians prior to beginning the interviews. Interviews are expected to last 30-45 minutes and will be recorded and transcribed verbatim.

#### 8.2.6 DATA ANALYSIS

Interview data will be entered into Framework, a matrix based approach, which facilitates rigorous and transparent data management. The method involves five distinct, but highly interconnected stages: familiarisation; identifying a thematic framework; indexing; charting; mapping and interpretation. The approach enables data to be examined within cases across a range of different themes, thereby facilitating comparisons to be made both between different models of retrieval and within PICRTs. Use of Framework is also well suited to research involving group- and individuallevel analysis. The data will be managed using NVivo, a qualitative data analysis programme. Questionnaire data will be analysed using descriptive statistics to describe and compare the different PICRT models and to examine associations between key variables (frequencies, medians and inter-quartile ranges, Spearman's correlations, Mann-Whitney, Chi-squared and Kruskall-Wallis analysis of variance, as appropriate).

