# **3 STUDY SYNOPSIS**

Title	Critically ill children and young popplay do national Differences in access to			
Inte	Critically ill children and young people: do national Differences in access to			
	Emergency Paediatric Intensive Care and care during Transport affect clinical			
-	outcomes and patient experience? The DEPICT study			
Sponsor name	Great Ormond Street Hospital NHS Foundation Trust			
Primary	To study how clinical outcomes of critically ill children transported to			
objective	paediatric intensive care (PIC) are affected by national variations in			
	timeliness of access to paediatric intensive care.			
Secondary	1. To study how the experience of critically ill children (and their families)			
objective (s)	transported to paediatric intensive care are affected by national			
	variations in timeliness of access to paediatric intensive care.			
	2. To study how clinical outcomes of critically ill children transported to			
	paediatric intensive care are affected by national variations in care			
	provided by PIC retrieval teams (PICRT) during stabilisation and			
	transport.			
	3. To study how the experience of critically ill children (and their families)			
	transported to paediatric intensive care are affected by national			
	variations in care provided by PIC retrieval teams (PICRT) during			
	stabilisation and transport.			
	4. To study the relative cost effectiveness of current PICRTs.			
	5. To use mathematical modelling to evaluate whether alternative models			
	of PICRT service delivery can improve clinical and cost effectiveness.			
Study Design	Mixed methods study including a) quantitative analysis of linked routinely			
	collected PICANet audit data, b) qualitative study involving questionnaires			
	and interviews of critically ill children transported to intensive care and their			
	families, clinicians and managers, c) health economic analysis and d)			
	mathematical modelling.			
Study Endpoints	Primary outcome: 30-day mortality			
	Secondary outcomes: Mortality in PICU, at 90 days and within the first year			
	after the index PICU admission; length of stay in PICU; Resource use in PICU			
	(days on invasive ventilation, vasoactive agent therapy, renal replacement			
	therapy and extra-corporeal life support); length of hospital stay for the			
	index admission; number of hospital admissions and days in hospital in the			
Comple Ci-c	12 months following the index PICU admission.			

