## 5.2 Study objectives

1.1: To perform a quantitative analysis using linked routinely collected audit data to study the association between timeliness of access to paediatric intensive care and clinical outcomes in a national cohort of critically ill children transported to PICU.

[Timeliness of access to intensive care will be measured by a) time from referral to arrival of a PICRT at the patient's bedside, and b) time from referral to PICU admission].

1.2: To perform a quantitative analysis using linked routinely collected audit data to study the association between care delivered by PICRTs and clinical outcomes in a national cohort of critically ill children transported to PICU.

[We will study specific aspects of PICRT care such as team composition, interventions performed and critical incidents during transport].

1.3: a) To explore, using qualitative methods (individual interviews and workshops) and questionnaires, the experiences and perspectives of a purposively sampled national cohort of parents of transported critically ill children.

b) If and where feasible, to use innovative methods to explore the experiences of transported critically ill children.

- 1.4: To explore, using qualitative methods (individual interviews and workshops), the experiences and perspectives of a purposively sampled national cohort of clinicians from a range of settings (acute general hospitals, PICRTs and PICUs) and service managers/NHS commissioners.
- 2.1: To perform cost effectiveness analyses of PICRT provision for critically ill children, comparing different service models currently in use.
- 2.2: To use mathematical modelling and location allocation optimisation methods to explore whether alternative models of service delivery for PICU/PICRT services can improve clinical outcomes while remaining cost effective.
- 2.3: To synthesise study findings to inform the development of evidence-based national standards of care and information resources for families and clinicians.

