#### 8.1.1 STUDY DATASET

We will generate a linked dataset for the study from several data sources:

1. National paediatric intensive care audit data from the Paediatric Intensive Care Audit Network (PICANet, www.picanet.org.uk).

PICANet is commissioned by the Healthcare Quality Improvement Partnership (HQIP) as part of the National Clinical Audit Programme and is based at the Universities of Leeds and Leicester. PICANet data contain detailed clinical information regarding the case mix (age, diagnosis and severity of illness), resource use (daily organ support interventions) and outcome (such as length of PICU stay and vital status at discharge) of critically ill children. Detailed data regarding the transport are also included in PICANet. Data quality is ensured using precise rules and definitions applied by trained local data collectors at each participating unit, and both local and central validation checks to ensure completeness, logic and consistency.

2. Hospital Episode Statistics (HES, http://content.digital.nhs.uk/hes)

Administrative data related to A&E attendances and inpatient admissions to NHS Trusts in England are routinely collected as part of the HES Admitted Patient Care (APC) and Accident & Emergency (A&E) datasets. HES data contain demographic information (age, gender, ethnicity), clinical information (diagnoses and procedures), geographical information (address, site of treatment) and administrative information (time waited in A&E, hospital length of stay). Automatic data cleaning rules are completed at various stages in the cleaning and processing cycle. Similar APC and A&E data for Wales can be accessed from the NHS Wales Informatics Service's Information Services Division as part of the Patient Episode Database for Wales (PEDW).

3. Death registrations, ONS (http://content.digital.nhs.uk/onsmortality)

The Office for National Statistics collects data regarding the date and cause of death, as well as location of death, as part of death registrations in England and Wales. These data can also be accessed through the HES-ONS linked mortality data set.

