1) Identifying potential confounding variables and selection of variables for model development In the first instance, we will draw upon the expertise of clinical applicants and PICANet to generate a list of potential confounding factors. We expect the main confounding variables to be severity of illness (main diagnosis leading to PICU admission, ventilation status at referral and the Paediatric Index of Mortality 2 score) and the receipt of intensive care interventions prior to the PICRT arriving at the patient bedside. Intensive care interventions carried out by the general hospital team prior to the arrival of the PICRT are recorded in PICANet; we will also include as confounders the time spent at general hospital prior to being referred/accepted for transport to PICU (from linked HES data), and care provided in an adult intensive care unit (from linked CMP data). We will seek additional input from clinical applicants at monthly PMG meetings during months 4-12 of the project to further refine this list. We have also scheduled a Study Steering Committee (SSC) meeting during months 4-6, at which clinical members (medical/nursing/allied health professionals) will help further refine the list of confounders. In this way, we will obtain extensive expert clinical input into the choice of potential confounding variables that could be included in the model development; we will also generate clinical knowledge regarding the mechanisms by which variables may influence the exposure status and outcome.

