## 8.2 Workstream B: Qualitative and questionnaire study

This work stream will address the following two objectives of the DEPICT study: Objective 1.3: To explore parents', and where feasible children's, experiences of emergency transport to PICU, and

Objective 1.4: To explore clinicians' and service managers'/commissioners' perspectives of PICU transport and its impact on care provided to critically ill children and young people, and the wider impact on other patients and services.

We will employ a mixed-methods approach with a convergent triangulation study design whereby quantitative and qualitative data will be collected concurrently, with equal weight being given to both work streams. We will integrate findings from the qualitative and questionnaire study (how do national variations in the timeliness of access to emergency intensive care and care delivered by PICRTs affect patient/family experience?) with findings from the quantitative study (how clinical outcomes are affected by national variations) at the interpretation stage to generate complementary views of paediatric retrieval. Uniquely, the qualitative study will gather rich narrative detail from patient experiences and clinician perspectives that cannot be obtained from quantitative analyses of routine data.

See Appendix D for schedule of procedures involved in the qualitative and questionnaire study. See Appendix E for the data flow involved in the qualitative and questionnaire study.

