The questionnaire will seek parental responses to specific questions regarding their experience during and after their child's transport to PICU. We will cover aspects such as how long they waited for a PICRT to arrive, what information was provided regarding the transport process, expectations of the transport and whether these were met, medical staff involved from the PICRT, whether parents were able to accompany their child in the ambulance, duration and experiences of the journey and handover on arrival at the PICU, and whether they felt informed and involved in their child's care. We will use a mixture of rating scales, tick box questions and free text boxes; the questionnaire will be designed to take no longer than 15 minutes to complete. We will pilot the questionnaire first to ensure that it is acceptable to parents. Parents will be given a reply-paid envelope to return the questionnaire directly to the study team or, if they prefer, they will be able to return the questionnaire to a study collection box on the PICU.

Since postal response rates to questionnaires are typically about 20-25%, we anticipate receiving 800-1000 completed questionnaires (around 4500-5000 critically ill children are transported to PICU by PICRTs each year). We will link data from the questionnaires with PICANet audit data collected for that particular transport to provide additional information for the analysis (e.g. time to arrive at bedside).

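### The questionnaire analysis in 8.2.6 is entirely unadjusted, while the secondary objectives ask how timeliness and retrieval-team care affect family experience; its associations are open to confounding by case mix

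*Protocol*

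**What the plan says.** Section 8.2.6 fixes the questionnaire analysis: "Questionnaire data will be analysed using descriptive statistics to describe and compare the different PICRT models and to examine associations between key variables". The methods are frequencies, medians with interquartile ranges, and "Spearman's correlations, Mann-Whitney, Chi-squared and Kruskall-Wallis analysis of variance, as appropriate". No section gives an adjusted, stratified or multilevel analysis of these data.

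The questions are worded as effects. Secondary objectives 1 and 3 in the synopsis begin "To study how the experience of critically ill children (and their families" and go on to ask how that experience is affected by variation in timeliness and in PICRT care. Section 8.2 gives the qualitative and questionnaire study the question "how do national variations in the timeliness of access to emergency intensive care and care delivered by PICRTs affect patient/family experience". Operational objective 1.3 in section 5.2 is softer: "To explore, using qualitative methods (individual interviews and workshops) and questionnaires, the experiences and perspectives".

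For the same exposures and clinical outcomes, section 8.1.3.4 says "We expect the main confounding variables to be severity of illness (main diagnosis leading to PICU admission, ventilation status at referral" and adds the PIM-2 score. It plans causal diagrams, multilevel regression, propensity scores and instrumental variables.

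The data needed for adjustment are within reach. Section 8.2.2 says "We will link data from the questionnaires with PICANet audit data collected for that particular transport to provide additional information for the analysis", with time to bedside as its only example. Section 8.1.1 says "PICANet data contain detailed clinical information regarding the case mix (age, diagnosis and severity of illness", and sections 8.2.1 and 9 seek consent to use the child's PICANet data.

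**The concern.** A two-variable test cannot separate the effect of a long wait, or of one PICRT model, from differences in the children concerned. The protocol expects illness severity to be related to timeliness. If severity also shapes how parents rate the transport, an unadjusted comparison could show an effect that is only case mix, or hide a real one.

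Section 8.2 gives the quantitative and qualitative strands equal weight and brings them together at interpretation. Confounder-adjusted results on clinical outcomes would then be read beside unadjusted results on experience, as answers to parallel questions. Under objective 2.3 and section 8.5, the synthesis is meant to inform national standards.

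**Working it through.** **Method against question.** The protocol states no power or error rate for the questionnaire, so there is no figure to reproduce. Each listed method describes one variable or relates two. The phrase on appropriateness selects among them and adds no other. The statistical analysis plan announced in section 8.1.3.4 is described as a step before the workstream A models. The mismatch with the effect wording is therefore in the protocol's own text.

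**Inputs from the protocol.** 800 to 1000 completed questionnaires (8.2.2). 85% of children reached within 3 hours, so 15% at 3 hours or more (8.1.3.5). I assume respondents have the same share.

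**Inputs assumed.** The protocol gives no association of severity with waiting time or with parents' ratings. All such values below are assumptions. Both illustrations set the true effect of delay to zero and treat questionnaires as independent.

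**Illustration 1: correlation of waiting time with rating.** If severity has correlation c with both, and they are otherwise unrelated, their unadjusted correlation is r = c × c. With the Fisher transformation, d = atanh(r) × √(N − 3), and the two-sided rejection probability at 5% is Φ(d − 1.96) + Φ(−d − 1.96). This treats the rank correlation as an ordinary one, which is an approximation.

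| c | r | d, N = 800 | P | d, N = 1000 | P |
|---|---|---|---|---|---|
| 0.1 | 0.01 | 0.28 | 6% | 0.32 | 6% |
| 0.2 | 0.04 | 1.13 | 20% | 1.26 | 24% |
| 0.3 | 0.09 | 2.55 | 72% | 2.85 | 81% |

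**Illustration 2: 3 hours or more against less, poor experience yes or no.** The groups are 120 and 680 at N = 800, and 150 and 850 at N = 1000. Suppose 10% of the late group and 40% of the early group are severe, and experience is poor in 40% of severe and 20% of other cases.

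- Late: 0.10 × 0.40 + 0.90 × 0.20 = 0.22.
- Early: 0.40 × 0.40 + 0.60 × 0.20 = 0.28.
- Crude odds ratio: (0.22/0.78) ÷ (0.28/0.72) = 0.73, although delay does nothing.
- Rejection probability in the direction of the bias: Φ((0.06 − 1.96 × SE0)/SE1). At N = 800, SE0 = 0.0440 (pooled) and SE1 = 0.0416 (unpooled), which gives 26%. At N = 1000 it is 32%.

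Variations with the same formulas:

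- Weaker imbalance, 20% against 30% severe: rates 0.24 and 0.26, odds ratio 0.90, rejection about 6% to 7%.
- Imbalance of 10% against 40%, with poor experience in 50% of severe cases: rates 0.23 and 0.32, odds ratio 0.63, rejection about 50% to 60%.
- No imbalance: no bias.

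Reversing the imbalance reverses the sign. Neither illustration covers comparisons of PICRT models.

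**Is adjustment feasible?** If 20% to 30% report a poor experience (assumed), there are 0.20 × 800 = 160 to 0.30 × 1000 = 300 events. At ten events per parameter, that is room for about 16 to 30 parameters.

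**The case against.** The strongest reply is that the questionnaire is a descriptive component. Section 8.2.6 calls the analysis descriptive and speaks of associations. Objective 1.3 says explore, and interviews and workshops share the objective. This stands in part: a reader might infer that the questionnaire alone answers secondary objectives 1 and 3, and it does not. But the synopsis and section 8.2 keep the effect wording, and 8.2.6 goes on to compare PICRT models. If only description is meant, the results need that label.

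A reader might also infer that the experience results will be confounded. The documents do not support that. Section 8.1.3.4 names severity as a confounder for clinical outcomes, and no section says it predicts parents' ratings.

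A further tempting step is that unadjusted questionnaire results would set the travel threshold in section 8.4.3. That section names the workstream B interviews, not the questionnaires.

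Finally, simple adjustment has limits. Section 8.1.3.4 warns that PIM-2 could mask an effect of timeliness. Section 8.2.2 lets both parents of a child respond, and section 7 gives only 10 PICRTs. The questionnaire was also still to be developed and piloted. These points are right. They shape the remedy and do not remove the need for one.

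**Conclusion.** The point holds as a mismatch between method and question. Section 8.2.6 provides only unadjusted associations, the objectives are worded as effects, and the linked data that would allow adjustment are already planned. The associations are open to confounding by case mix. How much, and in which direction, cannot be told from the protocol: over the assumed correlations of 0.1 to 0.3, a null effect would be declared significant in about 6% to 81% of studies, so the bias may be negligible or serious. The listed tests could not show which.

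**What to change.** In section 8.2.6:

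- Keep the listed tests as description.
- For time to bedside and for PICRT care or model, add ordinal regression for rating scales and logistic regression for yes/no items. Settle the exact forms once the questionnaire is final.
- Adjust for linked PICANet values fixed before the PICRT arrives: age, main diagnosis, ventilation status at referral and pre-existing condition. Use PIM-2 only in a sensitivity analysis, given the caution in 8.1.3.4.
- Account for two parents answering for one child and for clustering by PICRT. State that comparisons of PICRT models are limited by having 10 teams.
- Report crude and adjusted estimates together, and base any effect statement for secondary objectives 1 and 3 on the adjusted ones. Otherwise, label the questionnaire results as unadjusted and descriptive.

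The cost is a change of wording and modest extra analysis. No new data collection is needed, since consent and linkage are already planned. The drawback is that questionnaires that cannot be linked drop out of the adjusted models or need imputation.
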